7.6.3 Vital Signs and Weight

Vital sign results including blood pressure, pulse, and temperature will be included in the subject data listings.

7.6.4 12-Lead Electrocardiogram

Maximum post-baseline and maximum increase from baseline categories of corrected QT interval results will be summarized.

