laboratory assessments should be instituted. Correction of electrolyte abnormalities, monitoring of renal function and fluid balance, and administration of therapeutic and supportive care, including dialysis, should be done as clinically indicated. In the setting of TLS, oprozomib treatment will be interrupted until resolution of all clinical and laboratory therapeutic abnormalities consistent with TLS.

All cases of TLS must be reported to **the Sponsor** as an SAE as outlined in the protocol.

Orthostatic Hypotension

Orthostatic hypotension has been reported in subjects taking oprozomib. The following guidelines should be employed in the management of subjects exhibiting orthostatic hypotension. Etiology should be sought, whether neurogenic, non-neurogenic or iatrogenic. Dose modifications should be taken in accordance with [Table 5](#) and [Table 6](#).

- For those subjects with orthostatic hypotension who are taking antihypertensive medications, the subject's dosage and use of antihypertensive agents should be evaluated and reassessed on an ongoing basis while on study.
- Fluid intake should be assessed to confirm the subject is getting appropriate hydration in accordance with protocol requirements of six to eight, 8-ounce glasses of fluids in the 24 to 48 hours prior to dosing and on all days of oprozomib dosing.
- Fluid status should be repleted to normal levels in subjects with orthostatic hypotension.
- If protocol requirements for oral intake of fluids are already being met, additional measures should be taken to increase blood pressure as per investigator discretion, such as increased oral intake, fludrocortisone (Fluorinef) or midodrine or others depending on the etiology. Holding the dose during toxicity and dose reduction upon resolution may be a consideration (see [Table 7](#)).
- Ongoing monitoring of fluid status is warranted and should be managed per investigator discretion.
- In addition, vital signs monitoring may be extended beyond the time periods specified in the Schedules of Assessments ([Appendix A](#), [Appendix B](#), [Appendix C](#), and [Appendix D](#)).

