7.1 VITAL SIGNS ASSESSMENTS

Vital sign measurements include orthostatic blood pressure, pulse rate, respiration rate, and temperature. Subjects should lie down for approximately 5 minutes and then have blood

pressure and pulse rate measured consistently in 1 arm or the other. This should be followed by having the subject stand and the blood pressure and pulse rate measurements should be repeated at 1 and 3 minutes. Any drop of 20 mm/Hg systolic 10 mm/Hg diastolic, or lightheadedness/dizziness between supine and standing blood pressure measurements would indicate orthostatic hypotension. Usually an increase in pulse rate of 10 beats/min is also associated with, but not required for, diagnosis of orthostatic hypotension. If the subject has orthostatic hypotension, please see [Section 6.6.1](#).

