10.3.3 SAFETY ANALYSIS

Safety and tolerability assessments will include extent of exposure to study treatment, AEs (including the DLT assessment period DLTs and SAEs), laboratory values, vital sign results, and ECGs. Safety data will be examined on an ongoing basis to ensure subject safety.

Extent of exposure to the study treatment will be summarized using descriptive statistics (n, mean, standard deviation, median, and range). Percent of subjects and number of cycles with dose holds and reductions will be calculated by treatment group.

Adverse events will be coded using MedDRA. Treatment-emergent AEs are defined as AEs occurring from the first dose of study treatment through 30 days after the last dose of study treatment. An AE that is present before the first administration of study treatment and subsequently worsens in severity between the first dose of study treatment and 30 days after the last dose of study treatment is also considered to be treatment emergent. Adverse events will be summarized by MedDRA system organ class and preferred term for the number and percentage of subjects who experienced the event. A subject reporting the same AE more than once will be counted only once when calculating (1) within a given system organ class and (2) within a given system organ class and preferred term combination. For such cases, the

maximum NCI-CTCAE toxicity grade and strongest causal relationship to study treatment for the event will be used in the incidence calculations. Treatment-emergent AEs will be tabulated to examine their frequency, severity, and relationship to study treatment. Additional summaries will be provided for SAEs and events resulting in the permanent discontinuation of treatment. All AEs will also be included in individual subject listings.

A listing of subjects who experience a DLT during the DLT assessment period of the dose- escalation portion will be generated along with the results associated with the PK/PDn parameters considered.

Laboratory parameters will be summarized using descriptive statistics and by postdose shifts relative to baseline. Vital sign results will also be summarized descriptively for each scheduled protocol time point. Changes will be calculated relative to the values collected at baseline, defined as the last assessment taken prior to the first dose of study drug on Day 1 of Cycle 1.

The analysis of the locally performed ECGs will involve descriptive statistics.

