
Appendix L (Example Amgen Pregnancy Notification Worksheet)
	
New text added
	 
The image shows the 'AMGEN Pregnancy Notification Worksheet'. It is a form for reporting pregnancy events. It includes sections for: 1. Case Administrative Information (Protocol/Study Number, Study Design), 2. Contact Information (Investigator Name, Phone, Fax, Email, Institution, Address), 3. Subject Information (Subject ID #, Gender, Date of Birth), 4. Amgen Product Exposure (Table with columns: Amgen Product, Date of time of description, Frequency, Route, Start Date), 5. Pregnancy Information (Pregnancy number, Estimated date of delivery, Date of last menstruation, Date of pregnancy test, Date of delivery, Date of last healthy, etc.). It also has a signature line and a date field.
	
Provide updated pregnancy reporting worksheet.

Appendix M (Example Amgen Lactation Notification Worksheet)
	
New text added
	 
The image shows the 'AMGEN Lactation Notification Worksheet'. It is a form for reporting lactation events. It includes sections for: 1. Case Administrative Information (Protocol/Study Number, Study Design), 2. Contact Information (Investigator Name, Phone, Fax, Email, Institution, Address), 3. Subject Information (Subject ID #, Date of Birth), 4. Amgen Product Exposure (Table with columns: Amgen Product, Date of time of breast feeding, Frequency, Route, Start Date), 5. Breast Feeding Information (Did the mother breastfeed or provide the infant with pumped breast milk while actively taking an Amgen product?, Infant date of birth, Infant gender, etc.). It also has a signature line and a date field.
	
Provide updated lactation reporting worksheet.

APPENDIX K SUMMARY OF CHANGES IN PROTOCOL 2012-001 AMENDMENT 3

The key changes in Amendment 3 are listed below:

1. Addition of the new Oprozomib ER formulation Tablets
2. Addition of the step-up dosing for dose escalation
3. Addition of additional clinic visits for safety assessments
4. Addition of PK and PD assessments based on new dosing and formulation
5. Addition of assessments of orthostatic hypotension and management
6. Updates to safety and efficacy information from oprozomib studies
7. Updates to Inclusion/Exclusion criteria
8. Updates to phototoxicity risk with oprozomib

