7.6.2 Laboratory Data

All available laboratory results will be included in the subject data listings.

Selected laboratory test results will be assigned toxicity grades using CTCAE 4.03. A summary of post-baseline grade 3 or higher laboratory toxicities will be provided. The laboratory parameters of interest for these summaries are:

Hematology (all decrease)	Serum Chemistry (increase except where noted)	
Hemoglobin	ALT	Albumin
Platelets	AST	Uric Acid
WBC	Alkaline Phosphatase	Sodium (increase, decrease)
Neutrophils (absolute)	Total Bilirubin	Phosphorus (decrease)
Lymphocytes (absolute)	Creatinine	Potassium (increase, decrease)
	Calcium (increase, decrease)	Magnesium (increase, decrease)
	Glucose (increase, decrease)	

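### SAP 7.6.3 turns the protocol's vital-sign summary into a listing without recording the change and plans no measured count of orthostatic hypotension; SAP 7.6.2 grades albumin only for a rise.

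*SAP*

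**What the plan says.** **Vital signs, analysis.** Protocol 10.3.3: "Vital sign results will also be summarized descriptively for each scheduled protocol time point". It adds changes from a baseline taken before the first dose. SAP 7.6.3: "Vital sign results including blood pressure, pulse, and temperature will be included in the subject data listings". The SAP plans nothing further for vital signs.

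**Vital signs, collection.** Protocol 7.1: "Vital sign measurements include orthostatic blood pressure, pulse rate, respiration rate, and temperature". Subjects are measured lying down, then standing at 1 and 3 minutes. The same section gives the criterion: "Any drop of 20 mm/Hg systolic 10 mm/Hg diastolic, or lightheadedness/dizziness between supine and standing blood pressure measurements would indicate orthostatic hypotension". Protocol 6.6.1 gives the reason for attention: "Orthostatic hypotension has been reported in subjects taking oprozomib". The key changes listed for Amendment 3, the version the SAP follows, include "Addition of assessments of orthostatic hypotension and management".

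**Laboratory data.** SAP 7.6.2 plans a summary of post-baseline toxicities of grade 3 or higher. The chemistry columns are headed "Serum Chemistry (increase except where noted"). Albumin has no note.

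**Departures.** SAP Section 1 says that changes to analyses planned in the protocol will be documented in the SAP.

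**The concern.** Safety and tolerability is a primary objective in both phases. The protocol collects readings aimed at a harm it says has been seen with this drug, and it states numeric limits. The planned output uses those readings only as individual records, so a reader of the report could not see a measured rate of postural drops by dose or schedule. The rate from adverse-event tables depends on whether sites recorded a drop as an event.

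The albumin entry is a smaller matter of the same kind. A direction rule in a table header decides what is counted, and it leaves out one direction for albumin with no stated reason.

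**Working it through.** The point rests on comparing the texts. The only arithmetic is a count of scheduled readings.

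**1. Protocol against SAP, vital signs.**

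| | Protocol 10.3.3 | SAP 7.6.3 |
|---|---|---|
| Summary by time point | Yes | No |
| Change from baseline | Yes | No |
| Subject listing | Not specified for vital signs | Yes |
| Count against the 7.1 limits | No | No |

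The first two rows are a departure from the protocol, and the SAP does not record it. The last row is a gap in both documents.

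**2. Readings scheduled in Cycles 1 and 2** (footnote c of Appendices A to D). Each dosing day listed there has four time points: pre-dose, 30 minutes, 1 hour and 2 hours.

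- 5/14: Cycle 1 Days 1 to 5 (5 days) + Cycle 2 Days 1, 2 and 5 (3 days) = 8 days. 8 × 4 = 32 sets, of which 8 × 3 = 24 are post-dose.
- 2/7: Cycle 1 Days 1, 2, 8 and 9 (4 days) + Cycle 2 Days 1, 2 and 9 (3 days) = 7 days. 7 × 4 = 28 sets, of which 7 × 3 = 21 are post-dose.
- With two standing readings per set, the post-dose chances to cross a limit are 24 × 2 = 48 and 21 × 2 = 42 per subject.

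These are maxima under the Amendment 3 schedule.

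**3. Who may lack these readings.** Amendment 3 is dated 26 June 2014. Protocol 1.4.3 reports 12 subjects on 5/14 and 13 on 2/7 already treated by May 2014: 12 + 13 = 25. Against about 60 planned for Phase 1b, that is 25/60 = 42%. Of these, 4 + 7 = 11 were still on study and could have later readings, but not necessarily from Cycles 1 and 2.

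**4. Route through adverse events.** SAP 7.6.1 counts treatment-emergent events as number and percentage of subjects by system organ class and preferred term, and SAP 7.1 presents summaries by schedule and dose group. A case entered as an adverse event is therefore counted. Protocol 7.1 sends the site from a qualifying drop to the management guidance in 6.6.1. Neither section says that the drop must itself be recorded as an adverse event.

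**5. Albumin.** SAP 7.6.2 names 13 chemistry parameters. Phosphorus is marked for decrease; sodium, potassium, calcium, magnesium and glucose are marked for both directions. The other seven (ALT, AST, alkaline phosphatase, bilirubin, creatinine, uric acid and albumin) take the header's default, increase. Under that rule the graded table can show no fall in albumin. The descriptive and shift summaries of laboratory data in protocol 10.3.3 are not carried into SAP 7.6.2 either, so they give no second route. Under protocol 9.1 a laboratory finding becomes an adverse event only if it needs corrective action or is judged clinically significant.

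**The case against.** The SAP serves an abbreviated report, where reduced output is expected. Protocol 9.1 defines an adverse event broadly enough to cover any unfavourable sign, and 9.3.1 requires prompt documentation. The laboratory-only filter does not apply to vital signs. A rate of reported orthostatic hypotension by schedule and dose will therefore exist. The protocol promised descriptive statistics, not a threshold count, so restoring its summary would not by itself count orthostatic hypotension. A count using only the blood-pressure limits also differs from the 7.1 criterion, which includes symptoms, and many readings per subject raise the chance of a crossing.

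Much of this stands. The threshold table is an addition, and its limits must be stated. The abbreviated format does not settle the matter, though: the SAP does not give it as the reason for dropping the vital-sign summary, and SAP 7.6.4 keeps a categorical summary of corrected QT, so a short threshold table fits the format.

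A reader might go further and infer three things that the documents do not support:

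- That these events are never counted. They are, if reported as adverse events.
- That the orthostatic readings are left out of the listing. SAP 7.6.3 does not name them, but its list is introduced as inclusive, and protocol 7.1 treats them as vital signs.
- That low albumin is a known harm of oprozomib. The documents do not say so. Expecting a fall is an inference from the vomiting, diarrhoea and decreased appetite described in 1.4.1.

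**Conclusion.** The point holds in this form. SAP 7.6.3 drops a summary that the protocol planned and does not record the change. No planned table uses the orthostatic readings, up to 32 sets per 5/14 subject and 28 per 2/7 subject in Cycles 1 and 2, to count a harm that protocol 6.6.1 says has been reported. SAP 7.6.2 excludes low albumin from the graded summary through its default direction. What is lost is the measured rate and any unreported cases; the adverse-event rate remains.

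The documents give no figure for how many measured drops go unreported, so the size of that loss cannot be stated. A measured rate by formulation may not be recoverable either, because the ER tablets were introduced broadly in the same amendment that added the readings. The albumin point rests on the table's own wording and is secondary. Neither point affects an efficacy result.

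**What to change.** **SAP 7.6.3.** Restore the protocol 10.3.3 summary. Add one table, by schedule and dose cohort, of the number and percentage of subjects with a post-dose supine-to-standing drop meeting the blood-pressure limits in protocol 7.1. The table should:

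- use subjects with orthostatic readings as the denominator and state it, since those treated before Amendment 3 may have none;
- split subjects by whether the pre-dose reading already met the limits;
- state that either limit, systolic or diastolic, is enough, if that is the intended reading of 7.1;
- note that symptom-only cases are not captured, that repeated readings raise the chance of a crossing, and that scheduled post-dose readings in Cycles 1 and 2 stop at 2 hours.

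**SAP 7.6.2.** Mark albumin (decrease).

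Amendment 4 says that the primary analysis and abbreviated report are complete. If so, provide these as supplementary tables, identified as added later.

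**Cost.** One or two tables and one word. The table needs no new data, but its threshold count is sensitive to the number of readings per subject.

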7.6.5 Prior and Concomitant Medications

All prior and concomitant medications will be coded using WHO Drug Dictionary. Concomitant medications are defined as medications with start date or end date on or after the date of first dose and before the date of the last dose + 30 days or are ongoing at the time of first dose. Prior medications are defined as medications with a stop date before the date of first dose.

Concomitant medications will be summarized by generic name.

7.6.6 Protocol Deviations

Protocol deviations will be included in the subject data listings. Major protocol deviations will be either captured on the designated eCRF (e.g., eligibility violations) or identified through data review and surveillance.

8 Statistical/Analytical Issues

8.1 Handling of Dropouts or Missing Data

The handling of dropouts and missing disease status assessments for the efficacy variables is described in their definitions.

Missing or partially missing dates will not be imputed at data level. However, assumptions for missing or partially missing dates for important variables will be made to allow inclusion of appropriate data records in the analyses.

If a medication date or time is missing or partially missing, so it cannot be determined whether it was taken prior or concomitantly, it will be considered as a prior, concomitant, and a post-treatment medication.

If the partial AE onset date information does not indicate whether the AE started prior to treatment or after the TEAE period, the AE will be classified as TEAEs.

If the start day of subsequent anti-cancer therapy is missing, it will be assumed to be the first day of the month.

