6.6.3 EXCLUDED CONCOMITANT MEDICATIONS

Concurrent therapy with an approved or investigative anticancer therapeutic is not allowed.

Glucocorticoid therapy that exceeds a cumulative dose of 160 mg of dexamethasone is not permitted within 14 days prior to enrollment. During the study, glucocorticoid therapy (in addition to dexamethasone) is permitted only at the discretion of the medical monitor to treat a concurrent medical condition (e.g., asthma, inflammatory bowel disease, or as an antiemetic, etc.).

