7.7 ASSESSMENTS AT END OF STUDY TREATMENT OR EARLY DISCONTINUATION

Early discontinuation and End-of-Study assessments must be performed any time within 30 days following the subject's last administration of study drug and prior to initiation of any other treatment.

For subjects who discontinue treatment for reasons other than progression, disease assessments **will no longer be required under protocol Amendment 4.**

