Appendix E SCHEDULE OF STUDY ASSESSMENTS: DISEASE RESPONSE EVALUATIONS

Assessment	Screening	Cycle 2	Every 2 Cycles	EOS/ WD ^a	At Progression	LTFU for subjects without PD
	-14 to -1	Day 1	Days 10–14			
Disease response assessment labs						Every 8 weeks
SPEP ^b	X		X	X		X
Serum immunofixation	X		X	X		X
SFLC ^b	X	X ^c	X	X		X
24-hr Urine sample: UPEP ^{b,d} urine immunofixation	X		X	X		X
β2 microglobulin	X					
Skeletal survey ^c	X			X ^f		X ^e
Plasmacytoma evaluation ^g	X			X ^f		X ^g
Bone marrow aspirate and biopsy, cytogenetics, and FISH analyses ^h	X			X ^f		
Optional Genomic Biomarker samples ⁱ	X				X	

CT = computed tomography, lab = laboratory, EOS = End of Study, FISH = fluorescence in situ hybridization, LTFU = long-term follow-up; SFLC = serum free light chain; SPEP = serum protein electrophoresis, UPEP = urine protein electrophoresis, WD = withdrawal (from study), WM = Waldenström macroglobulinemia.

Footnotes apply to Phase 1b and Phase 2.

^a All End of Study Treatment Assessments must be performed within 30 days following the subject’s last administration of study drug and before initiation of any other treatment.

For subjects who discontinue treatment for reasons other than progression, disease assessments **will no longer be required under Amendment 4.**

^b After screening, disease response assessments should be done every 2 cycles after all study drug (oprozomib and dexamethasone) doses have been taken in that cycle (e.g., Cycle 2, Days 10–14) OR on Day 1 of the next scheduled cycle (e.g., Cycle 3, Day 1; Cycle 5, Day 1; Cycle 7, Day 1). However, the time of assessment(s) should precede the Day 1 dose. The times of assessments and study drug dose must be recorded in the source documents. All subjects are required to complete SFLC assessments at each time point noted above. For subjects with ≥ SD after being on study for 26 cycles, Days 10–14 OR predose on Cycle 27, Day 1 (the next assessment would be on Cycle 30, Days 10–14 OR Cycle 31, Day 1).

^c For Cycle 2 only, SFLC specifically should be performed on Day 1. After this assessment, SFLC can be performed with the other assessments.

^d UPEP (on a 24-hour collection) is required; no substitute method is acceptable.

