7.5.2 Progression Free Survival

Progression free survival (PFS) is defined as number of months (one month = 30.4 days) between start of treatment and first evidence of documented disease progression or death (due to any cause), whichever occurs first. Disease progression will be determined using IMWG-URC and will be determined by the investigator.

$$PFS = \text{Earliest date of disease progression, death, or censoring} - \text{Date of first dose} + 1 \text{ and expressed in months}$$

The duration of PFS will be right-censored for subjects who meet 1 of the following conditions: 1) starting a new anticancer therapy before documentation of disease progression or death; 2) death or disease progression immediately after more than 1 consecutively missed disease assessment visit or; 3) alive without documentation of

disease progression before the data cutoff date. For such subjects, the analysis of PFS will be right-censored according to the conventions described in Table 1.

Table 1: Date of Progression or Censoring for PFS and DOR

Situation	Date of Progression or Censoring	Outcome
No baseline disease assessments	Date of first dose	Censored
New anticancer therapy started before documentation of PD or death	Date of last disease assessment prior to start of new anticancer therapy	Censored
Death or PD immediately after more than 1 consecutively missed disease assessment visit	Date of last disease assessment visit without documentation of PD that is before the first missed visit	Censored
Alive and without PD documentation	Date of last disease assessment	Censored
Death or PD between planned disease assessments	Date of death or first disease assessment showing PD, whichever occurs first	Progressed
Death before first disease assessment	Date of death	Progressed

PD = progressive disease

Kaplan-Meier method will be used to estimate the distribution of PFS and the median and other quartiles in addition to the corresponding two-sided 95% confidence intervals.

Duration of follow-up for PFS will be summarized according to the Kaplan-Meier estimate of potential follow-up also termed “reverse Kaplan-Meier” (Schemper 1996).

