7.5.3 Time to Progression

Time to progression (TTP) is defined as number of months between start of treatment to the first documentation of disease progression. Disease progression will be determined using IMWG-URC as assessed by the investigator:

$$TTP = \text{Earliest date of disease progression or censoring} - \text{Date of first dose} + 1$$

and expressed in months

The same censoring rules, except for death, as in analysis of PFS will be applied in calculation of TTP. Subjects who die prior to progressive disease will be censored at the date of last evaluable response assessment.

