7.5.5 Duration of Clinical Benefit Response

Duration of clinical benefit response (CBR) will be calculated for subjects who achieve a MR or better. For such subjects, the duration of CBR is defined as the time from first documentation of MR or better to disease progression or death due to any cause. Dates of progression and censoring will be determined as described for the analysis of PFS.

Duration of CBR = Earliest date of disease progression, death, or censoring - Date of first observation of MR or better before confirmation + 1 and expressed in months

The duration of CBR will be summarized descriptively using the Kaplan-Meier method. The quartiles of the Kaplan-Meier distribution will be used to estimate the median duration of CBR.

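### SAP 8.1 sets a missing start day of new therapy to the first of the month with no lower bound, so a progression documented later that month is censored

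*SAP*

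**What the plan says.** SAP 8.1 gives one rule for an incomplete start date of new treatment: "If the start day of subsequent anti-cancer therapy is missing, it will be assumed to be the first day of the month". It names no floor at the last dose, the last disease assessment or the PD date. The same section says dates are not imputed in the stored data, but then allows assumptions about them in the analyses, so the rule does act on the results.

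The imputed date feeds SAP 7.5.2, Table 1. The situation "New anticancer therapy started before documentation of PD or death" is censored at the "Date of last disease assessment prior to start of new anticancer therapy". Table 1 covers PFS and DOR. For TTP, SAP 7.5.3 says "The same censoring rules, except for death, as in analysis of PFS will be applied in calculation of TTP". For duration of clinical benefit response (CBR), SAP 7.5.5 says "Dates of progression and censoring will be determined as described for the analysis of PFS".

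The protocol fixes the order of events. Section 7.7 requires the end-of-study assessments within 30 days of the subject's "last administration of study drug and prior to initiation of any other treatment", and Appendix E, footnote a, repeats this. Section 6.6.3 adds: "Concurrent therapy with an approved or investigative anticancer therapeutic is not allowed". The SAP was written to Amendment 3; the Amendment 4 change summary (Appendix N) lists no change to the ordering requirement in 7.7.

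**The concern.** For a subject managed as the protocol requires, PD found at or before the end-of-study visit comes before new therapy. If the therapy month is known, the day is missing and PD fell after the first of that same month, SAP 8.1 places the therapy before the PD. Table 1 then replaces a documented progression with a censoring at an earlier assessment.

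The subject is censored because of having progressed, so the censoring is informative and tends to lengthen the Kaplan-Meier estimates. PFS, TTP and DOR are secondary endpoints estimated from a modest number of subjects per schedule. The ORR test does not use these dates.

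**Working it through.** **Plan's own figure.** The documents give no figure for this rule. The only power figure, 77% for ORR (n = 46, reject at 12 or more responders, 15% against 30%), reproduces as 0.767 by exact binomial and is not in question.

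**One subject (assumed dates).** First dose 5 January 2015, 4-weekly assessments, last PD-free assessment 25 May, PD at the end-of-study visit 22 June, new therapy 29 June recorded only as June 2015. SAP 7.5.2 counts days inclusively and uses a 30.4-day month.
- True order: event at (168 + 1)/30.4 = 5.56 months.
- Under SAP 8.1: start set to 1 June, before the PD, so censored at 25 May, (140 + 1)/30.4 = 4.64 months.

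**Share of PDs affected, given a missing day.** Assume PD is equally likely on any calendar day and new therapy starts g days later. In a month of L days, PD is wrongly censored on days 2 to L − g, that is L − g − 1 days (zero if negative). Four years hold 1,461 days in 48 months (28 of 31 days, 16 of 30, one of 29, three of 28).

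| Gap g (assumed) | Calculation | Share |
|---|---|---|
| 7 days | (1461 − 48 × 8)/1461 = 1077/1461 | 0.737 |
| 14 days | (1461 − 48 × 15)/1461 = 741/1461 | 0.507 |
| 21 days | (1461 − 48 × 22)/1461 = 405/1461 | 0.277 |
| 28 days | (28 × 2 + 16 × 1)/1461 = 72/1461 | 0.049 |

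Gaps spread evenly over 7 to 28 days give 0.392. Over 28 to 42 days only gaps of 28 and 29 contribute: (72 + 28)/(15 × 1461) = 0.005.

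**Imputed start on or before the last study dose.** Appendix E, footnote b, says "disease response assessments should be done every 2 cycles after all study drug (oprozomib and dexamethasone) doses have been taken in that cycle", or alternatively on Day 1 of the next cycle. The last dose of a cycle is dexamethasone on Day 9, so PD at a scheduled on-treatment assessment falls k = 1 to 6 days after it. The affected days per month are L − g − k. At g = 7 and the mean k of 3.5, (1461 − 48 × 10.5)/1461 = 957/1461, which is 957/1077 = 89% of the censored PDs. The figures for 14, 21 and 28 days are 84%, 70% and 23%. They hold only for scheduled on-treatment assessments. If PD is found at a visit spread evenly over 1 to 30 days after the last dose, they fall to about 39%, 27%, 16% and 5%.

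**Effect on medians (simulation, all inputs assumed).** 4,000 runs, exponential times, 28-day assessments, no deaths, and every progressor with a recorded new therapy. PFS used 46 subjects with a true median of 4 months; DOR used 14 responders (30% of 46) with a 6-month median.

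| Days missing, gap | Median PFS, months | Median DOR, months |
|---|---|---|
| 5%, 14 days | 4.58 to 4.67 | 6.81 to 6.94 |
| 20%, 7 days (worst case) | 4.54 to 5.20 | 6.79 to 7.85 |
| 20%, 28 days | 4.54 to 4.57 | 6.80 to 6.85 |

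Sampling variation spans about 2.8 to 6.5 months for PFS and 3.3 to 12.0 for DOR.

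**The case against.** The strongest reply is that the effect is unproven and likely minor. The documents give neither the missing-day rate nor the gap from PD to new therapy. Protocol Appendix H, footnote e, requires two consecutive assessments for PD based on M-protein, calcium or free light chains. If therapy waits for a second 4-weekly assessment, the share is about 0.005. That footnote sets no minimum spacing, however, so short gaps are also possible. At 5% missing and a 14-day gap, a repeat of 800 runs left the PFS median unchanged in 88%. Progressing subjects complete the study 30 days after the last dose (Protocol synopsis), so later therapies may go unrecorded. If half are recorded, with visit windows and 10% deaths assumed, the shift is 0.03 months. All of this stands as a limit on size.

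A reader might infer that the rule can only lengthen the durations. It need not: with realistic visit windows and an assumed 10% of deaths, 1–3% of simulated runs gave a shorter median, although the mean shift stayed upward.

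A reader might also infer that first-of-month imputation is wrong in itself. The documents do not support that. For PD found in later follow-up the true order is unknown, and censoring is defensible. Protocol 7.7 is also a requirement rather than data: SAP 7.2 expects some subjects without the visit, and SAP 7.6.6 expects deviations.

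None of this supplies a lower bound, and no other text limits the rule.

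**Conclusion.** The point holds for subjects with a known therapy month, a missing day, and PD documented after the first of that month at or before a compliant end-of-study visit. For them the stated rules drop a documented progression from PFS, TTP, DOR and duration of CBR. The share affected, about 74%, 51%, 28% or 5% for gaps of 7, 14, 21 or 28 days, rests on assumed gaps and on PD dates spread evenly over the calendar. The overall effect on medians is probably small, and ORR is untouched. It merits correction because it is a clear error of order and cheap to remove.

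Two stronger readings are not supported. One is that the imputed start usually breaches the ban on concurrent therapy in Protocol 6.6.3; the high percentages apply only to PD at scheduled on-treatment assessments. The other is that SAP 7.5, by naming PD collected at end of treatment, contradicts Table 1. SAP 7.5.2 defines PFS by the first documented progression and Table 1 dates it, which largely resolves that ambiguity.

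**What to change.** Amend SAP 8.1. If only the day is missing, impute the later of (a) the first of the recorded month and (b) the day after the end-of-study assessment, or the day after the last dose if there was no such visit. Apply the floor only when it falls in the recorded month, and not when a recorded deviation shows that new therapy began before the visit. In the example the imputed start becomes 23 June and the event at 5.56 months is kept. In general, PD on or before the visit cannot then follow the imputed start.

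The visit must be the main floor. With a last dose assumed 11 days before PD, a floor at the last dose alone still leaves 93%, 74%, 51% and 28% reversed at gaps of 1, 7, 14 and 21 days. Subjects without a visit are therefore only partly covered.

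Report one sensitivity analysis that reverses the order for same-month, missing-day cases.

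Protocol section 1 and Appendix N state that the analysis and abbreviated report are complete, so this should be a documented re-analysis of existing data that lists the subjects whose status changes. It needs a short text change, some programming and one extra run, with no new data collection. Medians may become slightly shorter, and an unrecorded early start of therapy would count as an event; the sensitivity analysis helps to show how much that matters.
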